8.3 Changes to Protocol-Defined Analysis

No changes to the protocol-defined analysis are planned at this time. Any changes will be detailed in the final PK report.

8.4 Imputation of BLQ Values

For the calculation of mean concentrations and generation of mean concentration versus time profiles, all BLQ values will be set to zero, except when an individual BLQ falls between two quantifiable values, in which case it will be treated as missing data.

For the PK analysis and individual concentration versus time plots, a concentration that is BLQ is assigned a value of zero if it occurs in a profile before the first measurable concentration. If a BLQ value occurs after a measurable concentration in a profile and is followed by a value above the lower limit of quantification, then the BLQ is treated as missing data. If a BLQ value occurs at the end of the collection interval (after the last quantifiable concentration), it is treated as missing data. If 2 BLQ values occur in succession after Cmax, the profile is deemed to have terminated at the first BLQ value, and any subsequent concentrations are omitted from PK calculations.

In circumstances where alternative approaches to handling BLQ data are necessary, the relevant modifications will be appropriately documented in the clinical study report or final PK report.

Baseline-corrected serum copper concentrations that are less than or equal to zero will be treated as zero for the calculation of summary statistics and in the noncompartmental analysis.

8.5 Imputation of Missing Data

No imputation of missing data is planned at this time. Any missing data imputations will be detailed in the final PK report.

8.6 Data Exclusions

No data exclusions are planned at this time. Any exclusions will be detailed in the final PK report.

8.7 Significant Figures

Concentration data and PK parameters will be generally reported to 3 significant figures. All associated summary statistics for these parameters will also be reported to 3 significant figures, except for N which will be reported as an integer. Discrete time parameters (such as Tmax) and associated summary statistics will be reported to 2 decimal places.

9. PART C – PHARMACOKINETIC AND STATISTICAL ANALYSES DURING EXTENSION PHASE

9.1 Noncompartmental Pharmacokinetic Analysis and Descriptive Statistics

All final PK analysis and reporting for the VeraCept data for the combined Treatment Comparison and Extension Phases will be performed according to applicable Nuventra standard operating procedures and protocol specifications as outlined in Section 8. Analyses of Extension Phase data will be conducted at sponsor-directed intervals (e.g., after a 2-year data cut) as well as at the end of the 5-year study.

PK parameters for uncorrected and baseline-corrected serum copper will be calculated as described in [Table 9-2](#).

Table 9-1. Pharmacokinetic Parameters

Parameter	Description
Combined Data from Treatment Comparison and Extension Phases (Treatment A, VeraCept IUD only)	
Cmax	Maximum observed concentration, observed by inspection of individual study participant serum concentration-time plots
Tmax	Time of maximum observed concentration, obtained directly from the observed concentration-time data
Cmean	Mean total serum copper concentration of samples collected after Day 1

Note that the abbreviations and definitions listed above may differ slightly from the protocol in the phrasing; however, the equations and methods used to generate these parameters do not differ from the protocol.

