6.1.6. Month 60 (± 30 days) or Exit Visit

- Vital signs and weight
- Pregnancy test (urine)
- PK sample collection
- Pelvic exam to confirm IUD placement/string check
- Transvaginal ultrasound, if clinically indicated to confirm adequate IUD placement
- VeraCept removal
 - The subject's preferred method of contraception will be provided
 - If the subject elects a non-hormonal method of contraception, a 14-day supply will be provided by the site
 - If the subject elects to use hormonal contraceptive pills, a one-month supply of hormonal contraceptive pills will be provided to the subject by the site for the first 2 weeks following VeraCept removal
 - The subject will also be provided with condoms to take with her as an extra precaution if the subject fails to acquire the contraception noted above
 - Subjects should be reminded to avoid conception within 7 days after VeraCept removal
- **ParaGard Subjects**
 - Subjects may continue ParaGard use per standard clinical care or have the device removed

- If ParaGard is removed, subject's preferred method of contraception will be provided as outlined above
- Prior and concurrent medication
- Adverse events

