3.2 Secondary Endpoints

The secondary endpoints related to the PK analysis are:

- Mean total serum copper concentration (Cmean), Cmax, and AUC0-56 days for baseline-corrected copper for each treatment.
- Total serum copper concentrations within each treatment for each assessment day for 56 days.
- Mean total serum copper concentration for observed and baseline-adjusted copper for each treatment over 5 years (Treatment A, VeraCept IUD only).

[figure not shown]

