5. PHARMACOKINETIC SAMPLE COLLECTION

5.1 Blood Collection and Sample Processing

Two blood samples for PK analysis will be collected within 28 days from Day 1, and at least 24 hours apart within this screening period (can be performed on Screening and Day 1 visits prior to IUD insertion) to establish baseline copper concentrations, on Day 1 prior to IUD insertion, on Day 3, approximately 48 hours after insertion, and on Days 8, 15, 22, 29, and 57 at approximately the same time of day as the prior PK collections. Following the PK collections on Day 57, the PK samples for Months 6, 12, 18, 24, 30, 36, and 48 will be collected within 30 days of the planned collection day. Approximately 3-5 mL of whole blood will be collected for each blood draw. The total volume collected from each subject for all PK samples will be approximately 20 mL.

Blood samples will be collected in containers appropriate for serum collection, such as a “red topped” tube, which does not contain an anticoagulant.

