9.2 Statistical Analyses

Following Day 56 (study Day 57/Extension Phase), serum copper concentrations will only be collected for the VeraCept treatment group. These data will be listed, and additional statistical analyses or data presentations may be performed as appropriate.

10. SAFETY DATA SUMMARY AND REPORTING DURING TREATMENT COMPARISON PHASE AND TREATMENT EXTENSION PHASE

During the study, the investigator or study site personnel will be responsible for querying and recording AEs and serious adverse events (SAEs), as detailed below. For the sponsor to fulfill safety assessment obligations, the investigator will have to report all SAEs to the study sponsor, whether or not they result from study participation, within 24 hours of learning of the event.

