4.1.4 Analysis Windows

For analysis purposes, early termination visits and unscheduled follow-up visits will be assigned analysis visits according to the analysis windows in the following table. This mapping applies to labs, vital signs, and all other data planned to be collected and analyzed by visit in the Study Data Tabulation Model (SDTM) finding domains. Where multiple measurements for a particular parameter appear within an analysis window, the result closest to target day will be used. If equidistant, the latter result will be used for the summary measure. All measures may not be used in the data summaries (e.g., 2 vital signs measures within the same analysis visit window), but all measurements will appear in the datasets and listings.

Table 4.1.4.1 Analysis Windows:

Scheduled Visit (Subject Visit Window)	Analysis Visit	Analysis Window Target Day	Analysis Window	
			Lower Bound	Upper Bound
Visit 1/Screening	Baseline	1	N/A	1
Visit 2 (Day 1)				
Visit 3 (Day 3± 24 hours)	Day 3	3	2	5
Visit 4 (Day 8± 1 day)	Day 8	8	6	11
Visit 5 (Day 15± 1 day)	Day 15	15	12	18
Visit 6 (Day 22± 1 day)	Day 22	22	19	25
Visit 7 (Day 29± 1 day)	Day 29	29	26	43
Visit 8 (Day 57± 3 days)	Day 57	57	44	120
Visit 9 (Month 6± 30 days)	Month 6	182	121	273
Visit 10 (Month 12± 30 days)	Month 12	364	274	456
Visit 8 (Month 18± 1 month)	Month 18	548	457	639
Visit 9 (Month 24± 1 month)	Month 24	730	640	822
Visit 10 (Month 30± 1 month)	Month 30	913	823	1004
Visit 12 (Month 36± 1 month)	Month 36	1095	1005	1278
Visit 14 (Month 48± 1 month)	Month 48	1460	1279	1642
Visit 16 (Month 60± 1 month)	Month 60	1825	1643	N/A

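### The combined-phase Cmean in PK SAP Table 9-1 gives 43% of its weight to the first 57 days of a 5-year follow-up, and no change estimate with a CI is prespecified for the stability objective

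*SAP*

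**What the plan says.** PK SAP 2.2 lists the long-term stability of copper after VeraCept insertion as a secondary objective. PK SAP 3.2 lists a matching endpoint: "Mean total serum copper concentration for observed and baseline-adjusted copper for each treatment over 5 years (Treatment A, VeraCept IUD only").

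PK SAP 9.1 gives the extension parameters in the table captioned 9-1 (its text calls it Table 9-2). The data are "Combined Data from Treatment Comparison and Extension Phases (Treatment A, VeraCept IUD only"). The parameters are Cmax, Tmax and Cmean, with Cmean defined as "Mean total serum copper concentration of samples collected after Day 1". The same section allows analyses at intervals the sponsor chooses, with a 2-year cut as the example, and at the end of 5 years.

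For statistical analysis of the extension, PK SAP 9.2 says: "These data will be listed, and additional statistical analyses or data presentations may be performed as appropriate".

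PK SAP Section 11 plans more than a listing:
- observed and baseline-corrected extension concentrations with summary statistics by collection time;
- mean and individual concentration-time plots across both phases;
- a shift table with an Extension Phase column.

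PK SAP 8.5 plans no imputation. PK SAP 8.4 sets negative baseline-corrected values to zero.

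**The concern.** The two phases are sampled at very different densities and for different purposes. The protocol's rationale places dense sampling in the first 60 days because copper release is highest then and falls mostly in that period. The extension is there to show whether copper stays stable for years. A plain average over the pooled samples lets the sampling schedule set the weights, so a few weeks count for almost as much as the remaining years.

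Two things are at stake. First, the only average-exposure parameter defined for the combined phases leans towards early copper, and its early share changes with the data cut and with how long a woman stays. Second, the stability objective has no named estimate of change: beyond descriptive displays, the choice of analysis is left open until the data are available.

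**Working it through.** The documents state no weight share for Cmean, so there is no plan figure to reproduce here. The sample-size figures (12 per group, 20 enrolled) do not bear on the point.

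**Inputs**
- Samples after Day 1 up to Day 57: "on Day 3, approximately 48 hours after insertion, and on Days 8, 15, 22, 29, and 57" (PK SAP 5.1), so 6.
- Extension samples before Month 60: "the PK samples for Months 6, 12, 18, 24, 30, 36, and 48 will be collected within 30 days of the planned collection day" (PK SAP 5.1), so 7.
- Final sample: protocol 6.1.6, "Month 60 (± 30 days) or Exit Visit", includes a PK draw, so 1. PK SAP 5.1 does not name Month 60.
- Target days (safety SAP 4.1.4): 182, 364, 548, 730, 913, 1095, 1460 and 1825, the last being "Visit 16 (Month 60± 1 month").
- Assumption: equal weights. The SAP does not use the word unweighted, but this is the natural reading of its definition.

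**Weight of the first 57 days** = 6 / (6 + extension samples)

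| Follow-up | Share |
|---|---|
| Full schedule | 6/14 = 42.9% |
| Month 60 not counted | 6/13 = 46.2% |
| Last sample Month 36 | 6/12 = 50% |
| Last sample Month 24, or a 2-year cut | 6/10 = 60% |
| Last sample Month 12, no separate exit draw | 6/8 = 75% |
| Month 12 plus a separate exit draw | 6/9 = 66.7% |

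Share of time at full follow-up: 57/1825 = 3.1%.

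**Response to late drift.** Suppose copper is unchanged to Day 57 and then drifts linearly by X to Month 60. X is hypothetical, as the documents give no drift size. At each extension visit the fraction of X reached is (day − 57)/1768. The eight numerators are 125, 307, 491, 673, 856, 1038, 1403 and 1768. They sum to 6661, and 6661/1768 = 3.77.
- Pooled plain mean: 3.77/14 = 0.27X.
- Mean of Months 6 to 60 only: 3.77/8 = 0.47X.
- Time-weighted mean (area over time from Day 1): (0.5 × 1768)/1824 = 0.48X.
- By-visit mean at Month 60: the full X.

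**Response to an early rise.** Suppose instead that copper is raised by E at all six samples to Day 57 and is back at baseline from Month 6.
- Pooled plain mean: 6/14 = 0.43E at 5 years and 6/10 = 0.60E at a 2-year cut.
- Time-weighted, linear trapezoids: the area is 1 + 54 + 62.5 = 117.5 E-days, giving 117.5/1824 = 0.06E at 5 years and 117.5/729 = 0.16E at 2 years.

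Here the pooled figure falls from 0.60E to 0.43E between the two reports although nobody's copper changed after Month 6.

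**Dependence on length of stay under drift X.** For a woman whose last sample is at Month 12, the two extension fractions sum to (125 + 307)/1768 = 0.244.
- Pooled mean: 0.244/8 = 0.03X, a gap of 0.24X from a completer.
- Extension-only mean: 0.244/2 = 0.12X, a gap of 0.35X.
- Time-weighted mean: (0.5 × 307 × 307/1768)/363 = 0.07X, a gap of 0.41X.

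Time weighting therefore corrects the front-loading. It does not make an average independent of follow-up when copper really drifts; for that, change has to be estimated by visit.

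**The case against.** A reader might infer that a late rise or fall would be hidden. The documents do not support that. The planned by-visit tables, plots and extension shift column would show it, and the Month 60 mean would carry the full drift. The baseline-corrected table also gives a by-visit mean rise from each woman's own baseline, with an SD.

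It is also fair to say that the 5-year endpoint is not explicitly tied to Table 9-1. In PK SAP 3.1 and 3.2 the primary and first secondary endpoints carry the label Cmean, and the 5-year one does not. It could mean average concentrations plotted over time. The link is a reasonable inference, since Cmean is the only average defined for the combined phases, but it remains an inference.

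Three further limits stand:
- 43% is less than half, so the parameter is not mostly an early-period average for a completer. Whether all six early samples are burst samples is debatable, because the protocol's in vitro testing has release stabilising by about Day 21.
- Women who ask for early removal follow the exit procedures, which include a PK draw, so the early-leaver shares without a separate draw are upper figures.
- No single 5-year average measures drift well: the time-weighted one shows less than half of X. An extension-only mean would also drop the first six months of an endpoint stated over 5 years.

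The extension is single-arm and descriptive, and no decision threshold depends on it. That limits the consequence but does not answer the point. The by-visit summaries use whoever remains at each visit. They give no confidence interval and no slope, and zero-truncation of the corrected values masks falls below baseline in that table.

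**Conclusion.** The point holds in a limited form. As defined, the combined-phase Cmean puts 43% of its weight on 3% of the time for a full schedule, and 60% on the same 57 days at a 2-year cut. It responds to a linear late drift at 0.27X against 0.48X for a time-weighted mean, which is 0.27/0.48 or about 56% of it. Its value also depends on the data cut and on length of stay.

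Separately, the stability objective has descriptive displays but no prespecified estimate of within-woman change with a confidence interval.

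This rests on equal weighting of samples, on the scheduled visit days, and on reading Table 9-1 as the implementation of the 5-year endpoint. The drift and early-rise profiles are illustrations, not forecasts. The primary VeraCept versus ParaGard comparison to Day 57 is unaffected.

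**What to change.** 1. In PK SAP Table 9-1, define the 5-year Cmean as a time-weighted mean: AUC from Day 1 to the last sample, divided by the observed time, for observed and baseline-corrected copper. Keep the pooled plain mean as a supportive parameter. State that this Cmean implements the 5-year endpoint in 3.2, and report follow-up length beside it.
2. In PK SAP 9.2, replace the open-ended provision with one prespecified repeated-measures mixed model on VeraCept observed concentrations, with visit, mean pre-insertion copper and a subject random effect. Report change from baseline at each visit and the Month 6 to 60 slope, each with a 90% CI, the level PK SAP 8.2 already uses. Observed values avoid the zero-truncation of the corrected data. Using all available visits handles dropout better than by-visit summaries, provided missingness depends only on what was observed.

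The cost is SAP wording, one parameter and one model, with no new samples or visits. With about 20 women at most, the intervals will be wide, and the analysis stays descriptive.

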9.2 Statistical Analyses

Following Day 56 (study Day 57/Extension Phase), serum copper concentrations will only be collected for the VeraCept treatment group. These data will be listed, and additional statistical analyses or data presentations may be performed as appropriate.

10. SAFETY DATA SUMMARY AND REPORTING DURING TREATMENT COMPARISON PHASE AND TREATMENT EXTENSION PHASE

During the study, the investigator or study site personnel will be responsible for querying and recording AEs and serious adverse events (SAEs), as detailed below. For the sponsor to fulfill safety assessment obligations, the investigator will have to report all SAEs to the study sponsor, whether or not they result from study participation, within 24 hours of learning of the event.

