11.1. Determination of Sample Size

The assumption is that there is no additional systemic exposure of copper when using the IUD. The primary analysis will use uncorrected total serum copper parameters (Cmax, Cmean, AUC0-56 days). A secondary analysis will be conducted using baseline-corrected total serum copper parameters (Cmax, Cmean, AUC0-56 days).

For the analysis using Cmax and Cmean, no formal hypothesis testing is being done. As such, a precision approach will be taken with boundaries chosen to reflect typical BE boundaries in the ln scale (plus or minus 22%). Assuming a normal range of 49 to 184 $\mu\text{g/dL}$, an estimate of the normal (mean) value could be close to 110-120 $\mu\text{g/dL}$. A comparable boundary would be plus or minus 22. This estimated mean with the added half-width still falls well within the normal range.

For the analysis using AUC0-56 days, no formal hypothesis testing is being done. As such, a precision approach will be taken with boundaries chosen to reflect typical BE boundaries in the ln scale (plus or minus 22%). AUC values will be ln transformed.

For a two-sided 90% confidence interval for a two-sample normal mean difference, assuming a common standard deviation of 25, a sample size of 12 per group is required to obtain a half-width of at most 22 $\mu\text{g/dL}$ with a conditional probability of at least 0.90 given that the interval contains the true mean difference. The actual probability is 0.95.

Assuming a maximum unevaluable rate of 40%, up to 20 subjects will be enrolled in each group. Replacement subjects may be enrolled, as needed, to ensure that at least 24 evaluable subjects complete the study

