2.2 Secondary Objectives

The secondary objectives of the study related to the PK analysis are:

- To assess the relative bioavailability of baseline-corrected total serum copper from VeraCept versus ParaGard based on Cmax, Cmean, and AUC0-56 days.
- To assess the total serum copper levels within each treatment relative to the normal range (49 to 184 $\mu\text{g}/\text{dL}$).
- To assess the long-term stability of copper levels following insertion of VeraCept.

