11.1.2 Post-text Tables

Caption	Comments	Notes for Programming
Summary of Subject Disposition by Phase and Treatment Group	
Separate columns for Treatment Comparison and Extension Phases, with the former presenting data for VeraCept, ParaGard, and Overall
 
Extension Phase column will present data for VeraCept subjects from the Treatment Comparison Phase who will continue in the Extension Phase
	
Shortcut: Custom
 
Previous Shortcut: Custom
 
S.VAR: Phase + Treatment Group
 
Update previous Day 57 table “Summary of Subject Disposition”

Subject Accountability Table for the Treatment Comparison Phase	Treatment Comparison Phase only	
Shortcut: AC
 
Previous Shortcut: AC1
 
S.VAR: Treatment

Serum Copper Concentrations (ng/mL) and Summary Statistics by Sample Collection Time and Treatment for the Treatment Comparison Phase	Treatment Comparison Phase only	
Shortcut: CT
 
Previous Shortcut: CT1
 
S.VAR: Treatment

Baseline-Corrected Serum Copper Concentrations (ng/mL) and Summary Statistics by Sample Collection Time and Treatment for the Treatment Comparison Phase	Treatment Comparison Phase only	
Shortcut: CT
 
Previous Shortcut: CT1
 
S.VAR: Treatment

Noncompartmental Pharmacokinetic Parameters for Serum Copper and Summary Statistics by Treatment for the Treatment Comparison Phase	Treatment Comparison Phase only	
Shortcut: PT
 
Previous Shortcut: PT1
 
S.VAR: Treatment

Noncompartmental Pharmacokinetic Parameters for Baseline-Corrected Serum Copper and Summary Statistics by Treatment for the Treatment Comparison Phase	Treatment Comparison Phase only	
Shortcut: PT
 
Previous Shortcut: PT1
 
S.VAR: Treatment

Subject Accountability Table for the Extension Phase	Include Treatment column to indicate all data belongs to VeraCept Treatment Group	Shortcut: AC Previous Shortcut: AC1 S.VAR: Treatment
Serum Copper Concentrations (ng/mL) and Summary Statistics by Sample Collection Time for the Extension Phase	Include Treatment column to indicate all concentrations belong to VeraCept Treatment Group	Shortcut: CT Previous Shortcut: CT1 S.VAR: Treatment
Baseline-Corrected Serum Copper Concentrations (ng/mL) and Summary Statistics by Sample Collection Time for the Extension Phase	Include Treatment column to indicate all concentrations belong to VeraCept Treatment Group	Shortcut: CT Previous Shortcut: CT1 S.VAR: Treatment

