11.2 List of Figures

11.2.1 In-text Figures

Caption	Comments	Notes for Programming
Mean Serum Copper Concentration vs Time Plot with Treatments Overlaid for the Treatment Comparison Phase (Linear Scale)	Separate line for each Treatment Treatment Comparison Phase only	Shortcut: SPO Previous Shortcut: SP1 S.VAR: Treatment

Mean Serum Copper Concentration vs Time Plot with Treatments Overlaid for the Treatment Comparison Phase (Semi-log Scale)	Separate line for each Treatment Treatment Comparison Phase only	Shortcut: SPO Previous Shortcut: SP1 S.VAR: Treatment
Mean Serum Copper Concentration vs Time Plot for the Combined Treatment Comparison Phase and Extension Phase (Linear Scale)	Combined data from Treatment Comparison and Extension Phases, VeraCept data only	Shortcut: SPO Previous Shortcut: SP1 S.VAR: Treatment
Mean Serum Copper Concentration vs Time Plot for the Combined Treatment Comparison Phase and Extension Phase (Semi-log Scale)	Combined data from Treatment Comparison and Extension Phases, VeraCept data only	Shortcut: SPO Previous Shortcut: SP1 S.VAR: Treatment

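### The planned observed-copper visit means for the five-year extension cover whoever remains, and no estimate of within-woman change is pre-specified for the stability objective

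*SAP*

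**What the plan says.** PK SAP 2.2 sets the objective: "To assess the long-term stability of copper levels following insertion of VeraCept". The matching endpoint in PK SAP 3.2 is mean copper over 5 years in the VeraCept arm, both observed and baseline-adjusted. There is no comparator after Day 57.

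For the analysis, PK SAP 9.2 states: "These data will be listed, and additional statistical analyses or data presentations may be performed as appropriate". The output lists in Section 11 go further:

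- a table titled "Serum Copper Concentrations (ng/mL) and Summary Statistics by Sample Collection Time for the Extension Phase" (11.1.2), with a baseline-corrected counterpart;
- an in-text figure titled "Mean Serum Copper Concentration vs Time Plot for the Combined Treatment Comparison Phase and Extension Phase (Linear Scale") (11.2.1), with a semi-log version, and baseline-corrected plots in 11.2.2;
- overlays of individual profiles across both phases (11.2.2), a shift table with an extension column (11.1.1), and per-woman Cmean, Cmax and Tmax over the combined phases (9.1 and 11.1).

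Concentration summaries use the PK concentration population (8.1), for which 6.2 requires a successful placement and at least one quantifiable post-insertion value. Section 8.5 says "No imputation of missing data is planned at this time", and 9.1 carries Section 8 over to the extension. Section 8.4 sets baseline-corrected values at or below zero to zero, both in summary statistics and in the noncompartmental analysis.

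**The concern.** Stability asks whether copper changes within a woman over time. A plot of observed visit means answers that only if the same women contribute throughout, or if those who leave resemble those who stay. Women whose device is removed early go to the exit visit (Protocol 6.1.7), and a lost device is not replaced (Protocol 5.4). The safety SAP expects losses: it tabulates discontinuation by year (4.5) and removal and expulsion by year (4.9.1.2). The Day 57 mean may therefore rest on up to 20 women and the Month 60 mean on fewer.

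With no control arm after Day 57, nothing in the data would separate a shift due to who stayed from a shift due to copper. A real drift could equally be offset by the change in the group. Because further analysis is optional and extension data are cut at intervals the sponsor directs (9.1), an estimate of change could also end up being chosen after the data have been seen.

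**Working it through.** **The plan's own figure.** Protocol 11.1 works with a 90% interval for the two-arm difference and an SD of 25 µg/dL. It concludes that "a sample size of 12 per group is required to obtain a half-width of at most 22" (in µg/dL), and reports the conditional probability reached with that number as 0.95. The half-width is t(0.95, 2n-2) × S × √(2/n). At n = 12 with S = 25 it is 1.717 × 25 × 0.408 = 17.5. The probability of a half-width of at most 22, given coverage, is 0.954 at n = 12 and 0.897 at n = 11. Then 12/(1 - 0.40) = 20 per group. The figure is reproduced. It concerns the two-arm comparison to Day 57; no corresponding figure is given for the extension.

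**Assumptions, none in the documents.** 10 of 20 women remain at Month 60. Between-woman SD is 23 and within-woman SD 10 (√(23² + 10²) = 25.1, close to the plan's 25). The correlation r between a woman's copper level and staying is 0.3 to 0.5. Baseline is the mean of three samples, as in PK SAP 8.1.

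**Observed visit means, level-linked dropout.** If the 10 lowest of 20 normal values are kept, their mean lies 19.15 below the full mean when the SD is 25, that is 19.15/25 = 0.766 SD. With correlation r the expected shift is r × 23 × 0.766:

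- r = 0.3: 5.3 µg/dL
- r = 0.5: 8.8 µg/dL

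The direction depends on whether high- or low-copper women leave. If high-copper women leave, a true rise of 10 shows as 10 - 5.3 = 4.7 or 10 - 8.8 = 1.2. Purely random loss gives no average shift, but a chance composition effect with SD 23 × √(1/10 - 1/20) = 5.1.

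**A second set of assumptions.** Simulation used total SD 25, within-woman correlation 0.5 to 0.9, loss from 20 to 12 women, and correlation 0.6 between leaving and copper level. Apparent change from Day 57 to Month 60, in µg/dL:

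| True change | Observed visit means | Paired change in stayers | Mixed model |
|---|---|---|---|
| 0 | -6.5 to -8.8 | -0.1 to +0.2 | -1.2 to -0.2 |
| +10 | +1.2 to +3.4 | +10.0 to +10.1 | +8.7 to +9.7 |

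**Baseline-corrected visit means.** Each value subtracts the woman's own baseline, so level-linked dropout cancels: the apparent drift in the same simulations, including 60% loss, was -0.2 to +0.1. The zero floor is a different problem. The unfloored difference has SD √(100 + 100/3) = 11.55. With X normal, mean d and SD 11.55, the expected floored value is d × Φ(d/11.55) + 11.55 × φ(d/11.55):

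- d = 0: 4.6
- d = +10: 11.2, a movement of +6.6
- d = -10: 1.2, a movement of -3.4

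**Other displays.** A completer has 6 post-Day-1 samples by Day 57 and 8 afterwards, so 6/14 = 43% of her combined Cmean comes from the first 57 days. A woman leaving after Month 12 has 6/8 = 75%. Cmean averages over time and cannot show drift. The shift table registers only movement relative to 49-184 µg/dL, and the overlays carry no estimate.

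**Precision of the alternative.** With 10 women left, SD of the estimated change:

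- from the three-sample baseline: paired √((100 + 100/3)/10) = 3.7; unpaired 6.2;
- from Day 57: paired √(200/10) = 4.5; unpaired 6.4;
- from Day 57 at within-woman correlation 0.5 and total SD 25: 7.9 for both, so no gain.

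**The case against.** The strongest reply is that the plan offers more than visit means. Individual overlays and the shift table are within-woman displays, per-woman parameters are tabulated, and the number of non-missing values, accountability and disposition tables would make attrition visible. Half of the endpoint is baseline-adjusted, and those means are not distorted by level-linked loss. All of this stands, and it confines the composition problem under level-linked loss to the observed-copper summaries. None of these outputs supplies an estimate of change with an interval.

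A reader might infer that stability will be decided from the visit means. The documents do not say so: 9.2 commits to a listing and no display is named as decisive. A reader might also set the shifts against 22 µg/dL as a stability limit. That figure is a precision target for the two-arm comparison; no stability margin exists.

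It is also fair to say that no document links copper level to staying in the study, that five-year retention is not stated (the 40% is a sample-size allowance), and that this is a descriptive secondary objective in about 20 women. Protocol 1.2 itself doubts that serum copper can be attributed to the device beyond the initial period. These points limit the weight of the concern, but they do not supply the missing estimate.

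Finally, the synopsis defines an evaluable subject by complete sampling, including the extension for VeraCept women, which would imply a fixed group. PK SAP 6.2 and 8.1 nevertheless use the available-case population for concentration summaries.

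**Conclusion.** The concern holds for observed copper. The planned visit summaries and mean plots are available-case, and 9.2 pre-specifies no estimate of within-woman change. With 10 of 20 women left, level-linked dropout would move the observed mean by about 5 to 9 µg/dL with no change in any woman, or offset a real change of that order. The size rests on assumed retention, an assumed correlation of 0.3 to 0.5 and an assumed 23/10 split of the SD.

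It does not extend to every planned display. Baseline-corrected means are protected against level-linked dropout; their weakness is the zero floor, which mutes rises and, more strongly, falls. The main reason for a paired analysis is to remove the composition effect. The gain in precision depends on the within-woman correlation and can be nil.

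**What to change.** In PK SAP 9.2, pre-specify for observed copper the within-woman change from pre-insertion baseline and from Day 57 at each extension visit, without the zero floor. Estimate it from a repeated-measures mixed model with visit as a categorical fixed effect and woman as a random effect. Report each change with its 90% CI and the number of women at that visit, alongside the displays already planned. Add a version of the mean plot restricted to women with complete extension data, and reconcile the synopsis definition of evaluable with the population in PK SAP 6.2.

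The cost is SAP wording, one standard model and one extra display on data already being collected; visits and samples do not change. The limit should be stated openly. If leaving depends on a woman's own copper change, the model remains biased: with no true average change, by about -3 µg/dL at 40% loss and -4 to -5 at 60% (assuming correlation 0.6 between leaving and drift, and drift SD 10). A simple sensitivity analysis for that case should accompany it, for example assigning women who left a range of assumed changes after their last sample.
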